## 8.7 Futility Analysis

NA

### 9 Health Economic Evaluation

This study will use descriptive statistics to describe information (estimated cost, days, reasons) on any hospitalizations, emergency room visits, observation stays, urgent care visits, other physician office visits, and stays at skilled nursing facilities. This will be related to the outcomes and the type of device therapy that the patient received.

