## 2 Study Objectives

## 2.1 Primary Objective(s)

The primary objective of this study is to observe the rate of recovery of ventricular function (EF>35%) between 90 and 180 days in newly diagnosed HF with reduced EF patients who were prescribed the WCD while being initiated on their HF medications. This will be measured from EF closest to before hospital discharge, then at 90, 180 and 360-days after WCD start, regardless of continued WCD use, prior EF improvement, or ICD implantation. While approximately one-third of the patients will likely experience EF recovery in the first 90 days, we hypothesize that an additional 5-10% of patients will experience EF improvement between 90 and 180 days as GDMT is achieved. This would be considered clinically significant in terms of the potentially avoided ICD implantations. Outcomes will be tracked and reported for three pre-specified groups based on assessment of SCD risk at 90 days of WCD use:

- 1) Patient improved (EF >35%), SCD risk deemed to be negligible. These patients are expected to end WCD use and not receive an ICD.
- 2) Patient improved EF from start of WCD use (a positive change of at least 5 percentage points in EF), or has a borderline EF of 30-35%, but still has continued SCD risk (EF ≤ 35%). These patients are expected to continue to use the WCD for an additional 3 months.
- 3) Patient not improved from start of WCD use (no change or worsening of EF), EF<30% and has continued high SCD risk. Those on GDMT are expected to be evaluated for an ICD. Those not yet on GDMT may continue the WCD for an additional 90 days.

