## 2.3 Safety Objective(s)

The safety objectives will be to compare complications from extended use of the WCD with those of the ICD during the study timeframe.

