## 8.3.7 Safety Endpoint- Complication data from WCD or ICD

Descriptive statistics will be used to analyze the incidence of complications from WCDs and ICDs in this population. This will include inappropriate treatments, as well as any other complications that may lead to hospitalizations or death.

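### The WCD-versus-ICD summaries of resource use and complications make no allowance for day-90 EF and GDMT status, on which expected device use depends

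*Combined protocol and SAP*

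**What the plan says.** Two analyses set the devices side by side.

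- **Resource use.** Section 9 states: "This study will use descriptive statistics to describe information (estimated cost, days, reasons) on any hospitalizations", with the other types of care listed after it. It then adds: "This will be related to the outcomes and the type of device therapy that the patient received".
- **Complications.** Section 2.3, repeated in 3.4, sets the objective: "The safety objectives will be to compare complications from extended use of the WCD with those of the ICD during the study timeframe". The analysis in 8.3.7 is: "Descriptive statistics will be used to analyze the incidence of complications from WCDs and ICDs in this population".

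No adjustment or stratification is given for either. Section 8.4 refers back to the rest of the protocol and 8.5 is marked not applicable. Baseline characteristics are brought in for EF recovery (8.3.1) and, with EF recovery status, for mortality (8.3.6), but not here.

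Section 2.1 describes three day-90 groups and the device use expected in each:

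- Group 1, EF above 35%: "These patients are expected to end WCD use and not receive an ICD".
- Group 2, EF still 35% or less but up by at least 5 points, or borderline at 30-35%: "These patients are expected to continue to use the WCD for an additional 3 months".
- Group 3, EF below 30% and not improved: "Those on GDMT are expected to be evaluated for an ICD"; those not yet on GDMT may stay on the WCD for a further 90 days.

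Section 3.1.5 likewise expects continued WCD use where EF is 35% or less and GDMT has not been reached. Section 2.1 also promises that outcomes will be reported for the three groups.

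**The concern.** Patients who extend the WCD and patients who receive an ICD are expected to differ at day 90 in EF, in EF change and in GDMT status. The protocol's own background (1.3) treats these as prognostic. It cites a trial in which LVEF improvement went with lower total mortality, and a Medicare analysis in which patients on no GDMT died more often within a year even after adjustment. This is confounding by indication, and a larger sample does not reduce it.

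At stake is how the tables will be read. Section 1.4.1 justifies the study partly by the wish to confirm that the WCD benefits patients by allowing the ICD to be deferred. A crude table of admissions, cost or complications by device would be taken as evidence on that question. The primary endpoint is not affected.

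**Working it through.** The plan states no figure for these comparisons, so there is nothing to reproduce. The check has three steps.

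**1. Is there a link between the group reporting and the device comparisons?** Section 2.1 reports outcomes by day-90 group. Sections 9 and 8.3.7 mention neither the groups nor GDMT. The group definitions use GDMT only to separate expected device use inside group 3. The device summaries as written are therefore crude.

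**2. What can a crude contrast show when the device has no effect?** For each device, crude rate = sum over strata of (stratum share × stratum rate), with the same stratum rates for both devices. All rates and shares below are assumptions, because the documents give none.

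*Two strata, lower and higher risk, with the ICD group holding more of the higher-risk patients:*

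| Rate, lower / higher risk | Higher-risk share, WCD / ICD | WCD crude | ICD crude | ICD:WCD |
|---|---|---|---|---|
| 10% / 15% | 40% / 60% | 0.6×10 + 0.4×15 = 12% | 0.4×10 + 0.6×15 = 13% | 1.08 |
| 10% / 20% | 30% / 70% | 0.7×10 + 0.3×20 = 13% | 0.3×10 + 0.7×20 = 17% | 1.31 |
| 15% / 25% | 20% / 80% | 0.8×15 + 0.2×25 = 17% | 0.2×15 + 0.8×25 = 23% | 1.35 |
| 15% / 25% | 10% / 90% | 0.9×15 + 0.1×25 = 16% | 0.1×15 + 0.9×25 = 24% | 1.50 |
| 15% / 30% | 20% / 80% | 0.8×15 + 0.2×30 = 18% | 0.2×15 + 0.8×30 = 27% | 1.50 |

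*Three strata, splitting group 3 by GDMT as 2.1 does.* Assumed rates: group 2, 15%; group 3 on GDMT, 20%; group 3 not on GDMT, 30%.

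- WCD, 60% group 2 and 40% group 3 not on GDMT: 0.6×15 + 0.4×30 = 21%.
- ICD, 10% group 2 and 90% group 3 on GDMT: 0.1×15 + 0.9×20 = 19.5%.
- ICD:WCD = 19.5/21 = 0.93.

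A false difference appears in every row, and its sign depends on how EF and GDMT combine in each device group.

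**3. Is time at risk comparable?** Extended WCD use is expected from day 90 to day 180, which is 180 − 90 = 90 days. An ICD placed at day 90 can be followed to day 360, which is 360 − 90 = 270 days, or three times as long. Actual times will vary, since the WCD may be worn longer and ICDs may be placed later. Incidence per patient with no time denominator mixes this difference into the comparison. A patient who moves from WCD to ICD contributes to both, and neither section says how such a patient is counted.

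**The case against.** The strongest reply is that the study is observational, the analyses are labelled descriptive, no test or causal claim is attached to them, and 2.1 already promises reporting by day-90 group. Part of this stands: the group reporting is a partial stratification. But it is not tied to Section 9 or 8.3.7, and 2.3 makes comparison the stated objective, so the descriptive label does not settle how the result will be used.

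A reader might infer three stronger claims, and the documents do not support them.

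- *That the protocol assigns the device.* It states expectations. WCD therapy follows normal commercial practice (7.2). Early ICDs and refusals are followed and are not withdrawals (3.1.5, 5.4.1), and 10.3 does not count ICD receipt or refusal as a deviation. Some patients enter with an ICD placed before day 90 (4.1.3), which cannot have been chosen on day-90 EF.
- *That device type is little more than a relabelling of day-90 EF.* Among unimproved patients below 30%, GDMT status, not EF, separates the expected device use.
- *That the bias must favour extended WCD use.* The 0.93 example runs the other way. Patients not on GDMT may remain on the WCD, and 1.3 reports worse survival without GDMT.

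The reply is also right that the complications half is weaker. Section 3.4 counts inappropriate interventions and device-related complications, and 10.1.1 leaves out common HF events unless related to WCD wear. The hospitalisation examples above say little about such events. Section 8.3.7 is looser, taking in any other complications that may lead to hospitalisation or death, so some exposure to severity remains.

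**Conclusion.** The point holds in a limited form. The device summaries in Section 9 and 8.3.7 are crude, while expected device use after day 90 depends on EF and GDMT status. A WCD-versus-ICD difference therefore cannot be attributed to the device. Neither direction nor size can be obtained from the documents. The range of 0.93 to 1.50 rests wholly on assumed rates and case mixes with no device effect, and shows only that a false difference in either direction is plausible. The concern is clearest for resource use and weaker for device-related complications. It touches secondary and safety analyses only, and is worth correcting because the remedy is cheap.

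**What to change.** Amend Section 9 and 8.3.7 as follows.

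- Make the WCD-versus-ICD comparison only among patients with day-90 EF of 35% or less. Either stratify by day-90 group and GDMT status, or adjust for day-90 EF, EF change from baseline, GDMT status and ischemic versus nonischemic cause.
- Give rates per person-time on each device, and state how time and events are split for a patient who changes device.
- State where patients below 30% with a gain of 1 to 4 points belong in the analysis, since they fit none of the groups in 2.1. Use continuous EF adjustment or a named category.
- Report ICDs placed before day 90 separately, because their day-90 EF and GDMT status are measured after implantation. Report patients above 35% without a device separately too, and not as a device comparison.
- Give the number left out for missing day-90 EF, since 8.6.3 does not replace missing data.
- Where overlap is too thin, which is most likely in group 3, label the tables descriptive and non-comparative.

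The main inputs are already collected: day-90 echo, medications, ICD implantation and care use (6.2.1, Table 2 in 6.5, 12.1). The cost is SAP wording, a few more tables, and wider intervals where few patients overlap.

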## 10 Safety and Adverse Device Effects

#### 10.1 Definitions

All device related adverse effects will be recorded during the study. All adverse device effects (ADEs) will classified by the investigator as anticipated or unanticipated. An unanticipated ADE is any adverse effect not identified by nature, severity, or frequency prior to the study.

10.1.1 Common Anticipated Device Effects with Study Device

The following events are commonly reported in patients having HF and therefore should not be reported unless deemed related to WCD wear: dyspnea, fatigue, weakness, edema, chest pain, and a rapid or irregular heartbeat.

Common anticipated device effects that may be caused by WCD use are as follows: skin rash or irritation, sleeplessness due to WCD alarms occurring at night and inappropriate shocks, discomfort from the device.

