## 3.4 Safety Endpoints

The safety objectives will be to compare complications from extended use of the WCD with those of the ICD during the study timeframe.

- 3.4.1 Complication data from ICDs for those who receive an ICD, including inappropriate interventions or other ICD-related complications that may lead to hospitalization or death.
- 3.4.2 Complication data from WCDs, including inappropriate shocks or other WCD-related complications that may lead to hospitalization or death.

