## 6 Study Procedures

## 6.1 Subject Recruitment and Screening

### 6.1.1 Subject screening for WCD registry and study

Patients will initially be screened from the prescribed WCD patients and enrolled into the prestudy registry. At 90  $\pm$  14 of WCD use, study subjects will be identified and screened from the clinical site's pre-study registry participants. The sponsor may also assist in the screening process by maintaining a current list of WCD prescribed patients to be screened for the registry by each site. Registry participation is complete when the patient enters the HF Opt study, or ends WCD use.

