#### 10.1.2 Unanticipated Adverse Device Effect (UADE)

An unanticipated adverse event is any adverse device effect not identified by nature, severity or frequency prior to the investigation.

If the frequency of inappropriate shocks exceeds 3 per 100 patient months, the inappropriate shocks should be reported as unanticipated adverse device effect.

Any commonly reported adverse events in patients having HF, as mentioned above, should not be reported unless deemed to be related to WCD wear.

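### The symptom-reporting exception in Sections 10.1.1 and 10.1.2 names only the WCD, which conflicts with a safety objective that compares WCD with ICD complications

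*Combined protocol and SAP*

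**What the plan says.** **The comparison.** The single safety objective in Section 2.3 is to "compare complications from extended use of the WCD with those of the ICD during the study timeframe". Section 3.4.1 makes the ICD side a named endpoint: "Complication data from ICDs for those who receive an ICD, including inappropriate interventions or other ICD-related complications that may lead to hospitalization or death". Section 3.4.2 is worded in parallel for the WCD. Section 8.3.7 gives the analysis: "Descriptive statistics will be used to analyze the incidence of complications from WCDs and ICDs in this population".

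**The reporting rule.** Section 10.1.1 says that certain events common in heart failure "should not be reported unless deemed related to WCD wear: dyspnea, fatigue, weakness, edema, chest pain, and a rapid or irregular heartbeat". Section 10.1.2 refers back to the same events and says that they "should not be reported unless deemed to be related to WCD wear". The ICD appears in neither exception, and the anticipated effects listed in 10.1.1 are WCD effects only.

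**The general rule.** Section 10.1 opens: "All device related adverse effects will be recorded during the study". Section 10.2.1 makes investigators responsible for recording and reporting every adverse device effect, tells them to ask about such effects at each contact, and has related signs and symptoms grouped under a single diagnosis. Section 10 does not say whether the ICD is a device for these purposes.

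**Patients with an early ICD.** Section 4.1.3 admits patients enrolled in the registry after 01-March-2019 who received an ICD before 90 days of WCD use. Section 6.1.1 says: "Registry participation is complete when the patient enters the HF Opt study, or ends WCD use".

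**The concern.** A comparison of complications between two devices needs the same ascertainment rule on both sides. Here, a site that follows Section 10.1.1 to the letter reports chest pain or an irregular heartbeat when it is attributed to the WCD, and does not report it when it is attributed to the ICD. Taken alone, this rule pushes the ICD count down and makes the WCD look relatively worse.

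Events that were never recorded cannot be recovered at analysis, and Section 8.6.3 says that missing data will not be replaced. Two sites could also read Section 10 differently, one reporting ICD effects under the general rule and the other leaving them out under the exception. That would add between-site differences in ascertainment to the same table.

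**Working it through.** The documents give no complication rate and no power calculation for the safety comparison, so there is no figure to reproduce. The check sets the sections side by side.

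1. **Does the exception cover the ICD?** No. Both 10.1.1 and 10.1.2 condition on WCD wear alone.

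2. **Does the general rule cure this?** Not clearly; it depends on what *device* means in Section 10.
   - If it means the WCD only, Section 10 has no reporting rule for ICD effects, although 2.3, 3.4.1 and 8.3.7 need the data. The context leans this way: 10.1.1 is headed for the study device, Section 7 uses that term for the WCD, the Study Summary lists the WCD as the intervention, and 10.2.1 asks about the link with study treatment and whether it was discontinued.
   - If it includes the ICD, 10.1 and 10.2.1 require an ICD-related symptom to be recorded, while 10.1.1 and 10.1.2 say not to report it.
   - Either reading leaves a conflict.

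3. **Does the schedule fill the gap?** In part. Table 2 has a clinical-status row (care utilization, medications, symptoms, ICD implantation) and a row for ICD or WCD defibrillation data at every contact. Sections 6.2.4 to 6.2.7 collect adverse events, and Section 3.3.4 collects reasons for hospital, emergency and office visits. Neither Table 2 nor the data list in Section 12.1 has an item for ICD complications, and the symptom and utilization items do not ask which device, if any, was responsible.

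4. **Which events are exposed?** An ICD complication entered as a diagnosis is not on the symptom list. One that leads to hospitalization or death is within 3.4.1 and also appears in the utilization or mortality data. Inappropriate ICD therapy falls under the defibrillation row. What remains is mainly an ICD-attributed event seen only as a listed symptom, with no diagnosis and no admission.

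5. **Direction and size.** Suppose a share *f* of ICD complications is of this kind and is lost by every route, while WCD capture is complete. The observed ICD rate is then (1 − *f*) times the true rate, and the WCD:ICD ratio is inflated by 1/(1 − *f*). Assumed values of 10%, 25% and 50% give 1/0.90 = 1.11, 1/0.75 = 1.33 and 1/0.50 = 2.00. The documents supply no *f*, so these show the direction only and are not estimates.

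6. **Early ICD.** Table 1 has no ICD items. Visit 1 (Section 6.2.3) has no adverse-event line, unlike 6.2.4 to 6.2.7. Table 2 does collect clinical status and ICD defibrillation data at day 90, but no look-back to implant is stated. If an ICD is placed at day 30 and WCD use ends then, 90 − 30 = 60 days pass before the nominal visit (46 to 74 with the 14-day window) with no scheduled assessment of ICD complications.

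**The case against.** The best defence is that 10.1.1 is there to keep background heart-failure symptoms out of WCD reports and was never meant to govern ICD data. Section 3.4.1 requires those data in terms, 10.1 and 10.2.1 call for all device-related effects, and symptoms are to be grouped under a diagnosis. The case report forms (90D0109-CRF) are a separate document, not available here, and may already have an ICD complication field. Section 10.2.1 also asks for device model and serial number in the source record. Much of this stands, and it confines the problem to the residue in step 4. It does not remove the contradiction, because a site reads the protocol and the exception there is explicit.

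A reader might infer more than the documents support:

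- **That ICD complications are barred from reporting.** They are not; several sections require or capture them.
- **That the sponsor, as acting DSMB, would never see the affected events.** The sponsor is also the data coordination center and its staff review entered data weekly, including symptoms and utilization. The event may be visible, but without attribution to the ICD.
- **That losing registry patients who never enter the study biases the comparison.** Those patients are outside it. Section 3.1 starts the study at day 90, so whether ICD events before day 90 belong in the comparison at all is open. Section 6.3.1 also collects adverse events from registry patients at an unanticipated end of WCD use.

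**Conclusion.** The point holds as an internal contradiction with a consequence for ascertainment. Sections 10.1.1 and 10.1.2 conflict with 2.3, 3.4.1 and 8.3.7, and with 10.1 and 10.2.1 if *device* includes the ICD. Followed literally, they undercount ICD complications that appear only as a listed symptom. The size cannot be estimated from the documents. The direction assumes that sites apply the exception as written and that the forms do not separately ask for ICD-attributed symptoms.

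The early-ICD gap is a smaller, related weakness: post-implant complications before day 90 have no scheduled capture and no stated look-back.

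Severity is moderate to low. The safety analysis is descriptive, no test or decision rule depends on it, and the primary EF endpoint is unaffected.

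**What to change.** - In 10.1.1 and 10.1.2, change the condition so that it reads *related to the WCD or to an ICD*.
- State in Section 10 that an adverse device effect means an effect of either device, and record the attributed device on the form.
- Add a WCD/ICD complication row to Table 2 at each contact.
- For patients admitted under 4.1.3 with an ICD before day 90, have the day-90 form ask about complications back to the implant date. State in 8.3.7 whether those events count in the comparison.
- Check 90D0109-CRF first; if it already holds an ICD complication field, only the protocol wording needs to change.

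The cost is a short amendment, one eCRF field and somewhat more event reports from sites. No visits are added.

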#### 10.1.2 Unanticipated Adverse Device Effect (UADE)

An unanticipated adverse event is any adverse device effect not identified by nature, severity or frequency prior to the investigation.

If the frequency of inappropriate shocks exceeds 3 per 100 patient months, the inappropriate shocks should be reported as unanticipated adverse device effect.

Any commonly reported adverse events in patients having HF, as mentioned above, should not be reported unless deemed to be related to WCD wear.

## 10.2 Recording and Reporting of Adverse Device Effects

### 10.2.1 Investigator Recording and Reporting

The Investigators are responsible for recording and reporting all adverse device effects in the pertinent case report form (CRF). Adverse device effects must be reported to sponsor and reviewing IRBs per local reporting requirements.

The Investigator must next assess the seriousness of the adverse device effect.

#### Serious injury

Serious adverse device effects include any injury or event that is:

- Fatal or life-threatening, or
- Requiring or prolonging hospitalization, or
- Resulting in permanent impairment of a body function or permanent damage to body structure
- Necessitates medical or surgical intervention to preclude permanent impairment of a body function or permanent damage to a body structure

The Investigator should also assess whether the adverse device effect is anticipated or unanticipated.

At each contact with the subject, the investigator must seek information on adverse device effects by specific questioning and, as appropriate, by examination. Information on all adverse device effects should be recorded immediately in the source document, and also in the appropriate adverse effect module of the CRF. All clearly related signs, symptoms, and abnormal diagnostic procedures results should recorded in the source document, though should be grouped under one diagnosis.

All adverse device effects occurring during the study period must be recorded. The clinical course of each event should be followed until resolution, stabilization, or until it has been determined that the study treatment or participation is not the cause. Serious adverse device effects that are still ongoing at the end of the study period must be followed up to determine the final outcome. Any serious adverse device effects that occur after the study period should be recorded and reported promptly.

The minimum initial information to be captured in the subject's source document concerning the adverse device effect includes:

- Study identifier
- Study Center
- Subject number
- Device model and serial number
- A description of the event
- Date of onset

- Investigator assessment of the association between the event and study treatment
- Current status
- Whether study treatment was discontinued
- Whether the event is serious and reason for classification as serious

Serious adverse device effects should be reported to ZOLL immediately. The ZOLL contact persons for this study are:

In the United States:

[name], Clinical Research Project Manager [name] (office phone) [name] (fax) [contact] (email)

In Europe:

[name], Clinical Operations Manager EMEA [name] (office phone) [contact] (email)

The reviewing ethics committee must also be notified within 10 working days.

All other questions, complaints, or concerns regarding the WCD should be referred to ZOLL's customer support. These are not to be reported as adverse events.

